**Effects of 12-week Aerobic Exercise on Arterial Stiffness,
Inflammation, and Cardiorespiratory Fitness in Women with Systemic
LUPUS Erythematosus: Non-Randomized Controlled Trial**

NCT: NCT03107442

Document Date: 26/03/2024

Study Protocol and Statistical Analysis Plan

1. Objective

The primary aim of this study was to assess the effect of a 12-week aerobic exercise intervention following the ACSM guidelines on arterial stiffness in women with SLE in comparison with usual care. Secondary aims were to assess the effects of the exercise intervention on inflammation, oxidative stress, and cardiorespiratory fitness.

2. Design and Protocol Registration

This non-randomized controlled trial was registered at clinicaltrials.gov [NCT03107442] on 11 April 2017, before the enrolment of participants started (i.e., on 12 April), and no deviations occurred regarding the primary outcome and the secondary outcomes analyzed here.

3. Setting and Eligibility Criteria

Participants were recruited from the Systemic Autoimmune Diseases Unit of the “Virgen de las Nieves” and the “San Cecilio” University Hospitals. Women with a diagnosis of SLE according to the ACR criteria [26], a follow-up of 12 months, clinical and treatment stability during the previous six months, and not performing regular exercise (defined as 60 min/week of structured exercise) were included. Exclusion criteria were to have been under biological treatment in the previous six months or to need a prednisone dose of >10 mg/day; a background of CVD in the previous year; to present contraindications to perform exercise; other associated rheumatic conditions; pregnancy; active acute or chronic infection; neoplasms; acute renal failure; cardiac or pulmonary involvement; body mass index (BMI) >35; or not being able to read, understand, and sign written informed consent.

All participants received detailed information about the study procedures, and signed written informed consent. The Research Ethics Committee of Granada approved the protocol on 11 November 2016 (reference No.: 10/2016).

4. Procedures

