5.1.2. Control Group

After the baseline evaluation, the SLE patients assigned to the (usual care) control group received verbal information about a healthy lifestyle, including physical activity guidelines and basic nutritional information.

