Cardiorespiratory fitness was assessed with the Bruce submaximal treadmill protocol [37]. The test comprised five increasing workload stages of 3 min each (stage 1: 2.7 km/h and 10% inclination; stage 2: 4 km/h and 12% inclination; stage 3: 5.5 km/h and 14% inclination; stage 4: 6.8 km/h and 16% inclination; stage 5: 8 km/h and 18% inclination). The test concluded when the participant achieved 85% of the individual's HRmax, as

estimated with the formula by Tanaka et al. [29]. As validated SLE-specific formulas to estimate VO₂max are not available, we used the total time to reach 85% HRmax as the outcome of interest.

Other Measurements

All participants filled out a socio-demographic and clinical data questionnaire. Height (cm) was measured using a height gauge, weight (kg) with a bioimpedance device (InBody R20, Biospace, Seoul, Korea), and body mass index (BMI) was calculated (kg/m²). Blood pressure was measured with Mobil-O-Graph® (IEM GmbH, Stolberg, Germany) [36]. Disease activity was assessed through the Systemic Lupus Erythematosus Disease Activity Index (SLEDAI, range 0–105 where a higher score indicates higher degree of disease activity). Physical activity was self-reported at baseline and at week 12 with the International Physical Activity Questionnaire [38].

Sample Size

The sample size was calculated for the primary outcome (i.e., PWV). Ashor et al. found an average effect of aerobic exercise on PWV of $\square 0.63$ m/s in adults aged ≥ 18 years [21]. A total of 52 patients (26 per group) were needed to detect an effect of $\square 0.63$ (SD 0.75) m/s, with a power of 85% and an error of 0.05. Anticipating a maximum loss to follow-up of 15%, we aimed at recruiting a total of 60 patients.

Treatment Allocation and Blinding

Randomization was not feasible because more than half of the patients who regularly attend the Autoimmune Disease Units lived far from the Hospital and were not able to attend twice per week in case of being randomized to exercise. Therefore, participants from the city of Granada were included in the exercise group and participants living outside Granada were included in the control group.

To minimize potential selection bias, we aimed to match the groups by age (2 years), BMI (1 kg/m²), and SLEDAI (1 unit). The data analyzer was blinded to the patient allocation.

Statistical Analysis

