The distribution of the main study variables was assessed through histogram and Q-Q plots. As the main outcomes were non-normally distributed, their descriptive characteristics were presented using the median and interquartile range instead of the mean and standard deviation and we used non-parametric tests for the main analyses. Between-group baseline characteristics were compared with the Student t-test (when normally distributed) or Kruskal-Wallis test (when non-normally distributed) for continuous variables and the Chi-square test for categorical variables. The between-group differences in the studied outcomes were assessed through quantile regression with baseline values, resting heart rate (bpm) [39], and changes in physical activity (min/week; since the change in self-reported physical activity at week 12 was >60 min higher in the control compared to the exercise group and this change was associated with changes in PWV; rPearson = 0.27, p = 0.048) as potential confounders, after checking baseline group comparisons. As we aimed at assessing efficacy, the primary analyses were defined as per-protocol, where patients from the exercise group were included if attendance at the exercise sessions was 75%. To assess the robustness of the results, subsequent sensitivity analyses (i.e., baseline observation carried forward (BOCF) imputation; per-protocol with minimum attendance of 90%, and complete-case analyses) were conducted. A blinded investigator ([name]) undertook the data handling and all hypothesis testing. All the

analyses were conducted with Stata v.13.1 (StataCorp LP., College Station, TX, USA).

Statistical significance was set at $p < 0.05$.

Results

There were no between-group differences in the changes in arterial stiffness (median PWV difference $\Delta 0.034$, 95% CI $\Delta 0.42$ to 0.36 m/s; $p = 0.860$) or hsCRP, TNF-, IL-6, and MPO (all $p > 0.05$) at week 12. In comparison to the control group, the exercise group significantly increased cardiorespiratory fitness (median difference 2.26 minutes, 95% CI 0.98 to 3.55; $p = 0.001$). These results suggest that 12 weeks of progressive treadmill aerobic exercise increases cardiorespiratory fitness without exacerbating arterial stiffness, inflammation, or oxidative stress in women with SLE.

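### Every outcome is adjusted for a post-baseline change in physical activity chosen from trial data, and no listed sensitivity analysis is described as omitting it

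*Combined protocol and SAP*

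**What the plan says.** The aim in section 1 (Objective) is the effect of the programme "on arterial stiffness in women with SLE in comparison with usual care". Section 5.1.2 (Control Group) says that controls "received verbal information about a healthy lifestyle, including physical activity guidelines and basic nutritional information".

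The Statistical Analysis section gives one covariate set: "differences in the studied outcomes were assessed through quantile regression with baseline values, resting heart rate (bpm) [39], and changes in physical activity". It calls these potential confounders. The activity term is justified by two observed results. The first is a between-group gap: the term was included "since the change in self-reported physical activity at week 12 was >60 min higher in the control compared to the exercise group". The second is a correlation with the primary outcome, reported in these words: "this change was associated with changes in PWV; rPearson = 0.27, p = 0.048". Other Measurements gives the timing: "Physical activity was self-reported at baseline and at week 12 with the International Physical Activity Questionnaire".

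Under Treatment Allocation and Blinding, "participants from the city of Granada were included in the exercise group and participants living outside Granada were included in the control group". Robustness is assessed through "subsequent sensitivity analyses (i.e., baseline observation carried forward (BOCF) imputation; per-protocol with minimum attendance of 90%, and complete-case analyses".

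**The concern.** A confounder in a non-randomized comparison should be something that allocation cannot have influenced. Change in activity to week 12 does not meet that test on the information given. The supervised programme may have displaced other activity in the exercise group. The advice given to controls, which is part of usual care here, may have raised theirs. Living in or outside Granada may also have played a part. The documents do not separate these explanations, nor say whether self-reported activity counts the supervised sessions.

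If allocation changed activity, adjusting for it removes part of the effect named in the Objective. If an unmeasured factor drives both activity change and PWV, adjustment can create a difference that is not there. If residence explains the gap, adjustment may help.

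The term was also selected after seeing the between-group gap and the correlation with PWV. No correlation is given for fitness, hsCRP, IL-6, TNF or MPO, yet the same covariate set is given for all the studied outcomes. Readers cannot see how far any estimate depends on the term.

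**Working it through.** **Inputs from the documents.** r = 0.27, p = 0.048; activity gap stated only as more than 60 min, on a min/week scale; PWV difference -0.034 m/s, 95% CI -0.42 to 0.36, p = 0.860 (the minus signs are not legible in the text used here and are inferred from the interval); fitness difference 2.26 min, 95% CI 0.98 to 3.55; planning SD 0.75 m/s and planned effect 0.63 m/s (Sample Size).

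**Assumed.** S, the SD of activity change, is not given; 100 to 300 min/week is tried. The SD of PWV change is taken as the planning value.

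**Reproducing the printed figures.**
- With n = 54, t = 0.27 × √(52 / (1 − 0.27²)) = 2.02 and p = 0.0483. The printed p therefore fits about 54 patients, so the selection used roughly the trial's own follow-up sample.
- CI half-width = (0.36 + 0.42)/2 = 0.39; SE = 0.39/1.96 = 0.199; 0.034/0.199 gives p = 0.864, close to the printed 0.860.

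**Shift in the PWV estimate if the term is omitted.** Shift = r × SD(PWV change)/S × gap. Example: 0.27 × 0.75/100 × 60 = 0.122.

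| S (min/week) | SD 0.75, gap 60 | share of 0.39 | SD 0.58, gap 60 | SD 0.75, gap 120 |
|---|---|---|---|---|
| 100 | 0.122 | 31% | 0.094 | 0.243 |
| 150 | 0.081 | 21% | 0.063 | 0.162 |
| 200 | 0.061 | 16% | 0.047 | 0.122 |
| 300 | 0.041 | 10% | 0.031 | 0.081 |

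SD 0.58 is roughly what the interval implies: 0.199/√(2/27) × √(2/π), a normal approximation for median regression with 27 per group. Allowing for the fact that the pooled r itself contains the between-group gap barely changes the first column (0.118, 0.080, 0.060, 0.040 for positive r).

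**Resulting intervals**, half-width held fixed, SD 0.75, gap 60:
- r positive as printed: about -0.16 (-0.54 to 0.24) at S = 100; -0.07 (-0.46 to 0.32) at S = 300.
- r negative, if a sign was lost: about +0.09 (-0.30 to 0.48) and +0.01 (-0.38 to 0.40).
- Widest case in the table (gap 120, S = 100): -0.66 to 0.12 for positive r, -0.18 to 0.60 for negative r.

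All contain 0. The shift depends on gap and S only through gap/S. For positive r and SD 0.75, the upper limit reaches 0 when gap/S = 0.36/(0.27 × 0.75) = 1.78; the largest ratio in the table is 120/100 = 1.2.

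**Simulation.** Median regression with n = 54, SD 0.75, gap 60, without the other covariates, 300 runs each, gave mean shifts of 0.10, 0.06 and 0.02 for S = 100, 200 and 300. The shift in a single dataset varied with an SD of 0.14 to 0.16 (simulated SE 0.29, noisier than the trial's 0.20). In a large-sample simulation where an unmeasured factor drove both activity change and PWV and allocation had no effect on PWV, the adjusted model gave a false difference of 0.13, 0.06 and 0.04 m/s for S = 100, 200 and 300, while the unadjusted one stayed near 0.

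**Fitness.** No correlation is given, so the shift cannot be computed. As an illustration only, half-width 1.285 gives SE 0.656 and an implied SD of 0.656/√(2/27) × √(2/π) ≈ 1.9 min. Borrowing |r| = 0.27, the shift is 0.31 min at gap/S = 0.6 and 0.62 min at 1.2, both below the 0.98 needed to reach 0. With r = 0.5 and gap/S = 1.2 it is 1.15 min, which exceeds 0.98.

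**The case against.** The strongest reply is that the plan states an efficacy aim. Comparing arms at equal outside activity is a recognisable efficacy contrast: supervised treadmill exercise not offset by what controls took up themselves. In a non-randomized trial, if the gap came from residence, dropping the term would let that difference back in. The model without the term would still exclude exercise patients with low attendance and still compare residents with non-residents. The plan discloses the term and its rationale, and hypothesis testing was blinded.

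Part of this stands. The residence explanation cannot be ruled out, so the current model should stay in view, and a model without the term does not cure the other limits of the design. Those limits apply to both models, however. The plan uses efficacy only to justify the per-protocol population and nowhere defines an effect at equal activity change. Blinding does not make a covariate prespecified.

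Two points of reading are also fair. The plan gives no separate model for each outcome and no covariates for the sensitivity analyses. That the term enters every model is the natural reading of a single sentence covering the studied outcomes; that no sensitivity analysis omits it means only that none is described as doing so.

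The sizes are illustrative: a Pearson slope is applied to a median regression of outcomes the plan calls non-normal, and SD 0.58 is a residual SD rather than the SD of PWV change. Outside the table, gap 120 with S = 60 (ratio 2) gives -0.83 to -0.05, which excludes 0. With equal groups, though, such a gap alone contributes (120/2)² = 60² to the pooled variance, leaving no variation within groups if S is the pooled SD.

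**Conclusion.** The concern holds and should be fixed. The adjustment uses a post-baseline variable selected from trial results, and no analysis without it is described. The reported estimates may therefore differ from the exercise versus usual care effect in the Objective.

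For PWV the likely movement is modest: about 0.12 to 0.04 m/s at a gap of 60 min/week and 0.24 to 0.08 at 120, with SD 0.75 m/s and S from 100 to 300 min/week. Direction depends on the sign of r. The no-difference result would probably stand. What is less secure is how much benefit can be excluded: the printed lower limit of -0.42 rules out the planned 0.63 m/s reduction, whereas the widest tabulated case reaches -0.66. For fitness, the inflammatory markers and MPO the dependence is unknown. Confidence is high on what the plan does; the actual shift is known only by refitting, and no conclusion is shown to change.

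**What to change.** For every outcome:

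- Fit and report the quantile regression with baseline covariates only (the baseline outcome value, plus resting heart rate if it was measured at baseline) as the estimate of exercise versus usual care. State when resting heart rate was measured, because the Statistical Analysis section does not say.
- Show the current model beside it, labelled as adjusting for a post-baseline variable selected from the trial data.
- State that this change was made after results were known, and that the cause of the activity gap (programme, advice or residence) is unresolved.

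The cost is one extra regression per outcome on existing data, one comparison table and a short edit to the analysis and results text. Estimates may shift slightly. If the gap came from residence, the estimate without the term carries that difference, which is why both models are shown.

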5.2. Outcome Measures

Primary Outcome Measure: Arterial Stiffness

Arterial stiffness was assessed in a sitting position by PWV [9], using the Mobil-O-Graph® 24 h pulse wave analysis monitor (IEM GmbH, Stolberg, Germany), whose operation is based on oscillometry recorded by a blood pressure cuff placed on the brachial artery. The coefficient of variation (CV) of Mobil-O-Graph for consecutive PWV analyses is 3.4% and its intraclass correlation coefficient is 0.98 [0.96–0.99] [32]. This device has been largely shown to be valid and reliable for measuring PWV and central blood pressure in different populations [33,34], meets the accuracy requirements of the

British Hypertension Society (BHS) standard [35], and can be recommended for clinical use [36].

Secondary Outcome Measures

Blood Samples and Biochemical Analyses

Fasting blood specimens for biochemical and immunological tests were collected and routinely processed by the central laboratory of our hospital. Among other measurements, they included lipids, insulin (BioRad, Marne-la-Coquette, France), and a routine biochemical profile. The homeostatic model assessment for insulin resistance (HOMA-IR) was calculated (HOMA-IR = glucose (mmol/L) × insulin (U/L)/22.5).

Inflammatory Markers Serum high-sensitivity CRP was assessed by an immunoturbidimetric method using the ARCHITECT cSystems (MULTIGENT CRP Vario assay); the limit of quantitation was 0.2 mg/L and the upper limit for normal serum was 5 mg/L (coefficient of variation <6%). Interleukin 6 and TNF-, as well as myeloperoxidase (MPO; as marker of oxidative stress), were measured in plasma. Serum was initially separated by centrifugation and stored at $\square 70\text{ C}$.

Bioserum concentrations of IL-6/TNF- (pg/mL) and MPO (ng/mL) were measured by an immunoradiometric assay using commercial kits (MILLIPLEX MAP Kit Human High Sensitivity T Cell Magnetic Bead Panel (HSTMAG-28SK) and Human Cardiovascular Disease Magnetic Bead Panel 2 (HCVD2MAG-67K)), Millipore) following the manufacturer's instructions. Quantitative data were obtained by using the Luminex-200 system (Luminex Corporation, Austin, TX, USA), and data analysis was performed on Xponent 3.1 software (Austin, TX, USA). The detections limits were 0.73 pg/mL for IL-6, 0.43 pg/mL for TNF-a, and 0.024 ng/mL for MPO.

Cardiorespiratory Fitness

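### The claim that exercise does not worsen inflammation or oxidative stress rests only on non-significant tests, and the PWV part omits its confidence limit

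*Combined protocol and SAP*

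**What the plan says.** The conclusion in the Results section is "These results suggest that 12 weeks of progressive treadmill aerobic exercise increases cardiorespiratory fitness without exacerbating arterial stiffness, inflammation, or oxidative stress". It makes three no-worsening claims, which rest on one sentence of results.

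- **Arterial stiffness:** "There were no between-group differences in the changes in arterial stiffness", followed by a median PWV difference, its 95% CI and p = 0.860.
- **Inflammation and oxidative stress:** the same sentence continues with "hsCRP, TNF-, IL-6, and MPO (all $p > 0.05$) at week 12". Nothing else is given for these four markers. The first three are the inflammatory measures. The fourth stands for oxidative stress; under Inflammatory Markers the document refers to "myeloperoxidase (MPO; as marker of oxidative stress), were measured in plasma".

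The surrounding plan is built to look for differences. The Objective section sets out to assess effects on the secondary outcomes. The Statistical Analysis section says "As we aimed at assessing efficacy, the primary analyses were defined as per-protocol". The Sample Size section covers PWV only. No non-inferiority or equivalence margin, no hypothesis of no worsening and no power statement for any marker appears anywhere in the document.

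**The concern.** A test of difference that gives p > 0.05 has failed to detect an effect. It has not shown that a harmful effect is absent. That needs an interval whose unfavourable limit can be judged, ideally against a margin set beforehand. For the four markers the reader gets neither, yet two of the three outcomes in the no-exacerbation clause depend on them.

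A reader could take the sentence as reassurance that this exercise programme does not aggravate inflammation or oxidative stress in women with SLE. That is a safety-type statement, made from comparisons for which the study was not sized. PWV is better placed because an interval is printed, but the conclusion does not say how much worsening that interval leaves open.

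**Working it through.** **1. The plan's own sample size.** Inputs from Sample Size: difference 0.63 m/s, SD 0.75 m/s, power 85%, error 0.05 (two-sided assumed).

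n per group = 2 × (1.960 + 1.036)² × (0.75/0.63)² = 2 × 8.98 × 1.417 = 25.4, rounded up to 26, or 52 in total. This reproduces the stated figure. The calculation concerns detecting a PWV effect and says nothing about the markers.

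**2. The PWV interval.** Inputs from Results: estimate 0.034 in size, limits 0.42 in size and 0.36, p = 0.860. The minus signs were lost in text extraction.

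- Half-width = (0.36 + 0.42)/2 = 0.39.
- With a negative estimate: -0.034 ± 0.39 gives -0.424 to 0.356, which rounds to the printed limits. A positive estimate would give -0.356 to 0.424, which does not.
- SE = 0.78/(2 × 1.96) = 0.199. Then 0.034/0.199 = 0.171, so p ≈ 0.86, in line with the printed 0.860.

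The reading -0.034 (95% CI -0.42 to 0.36 m/s) is therefore coherent.

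**3. The direction of the PWV difference.** It is not labelled. The next sentence of Results reports fitness as higher in the exercise group with a positive difference (2.26 minutes, 95% CI 0.98 to 3.55), so the convention there is exercise minus control. If the same convention applies to PWV, the limit on the worsening side is 0.36 m/s. If it were reversed, the limit would be 0.42 m/s.

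**4. What p > 0.05 allows for a marker.** Using the normal approximation and taking a higher value as worse:

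- p > 0.05 means |estimate| < 1.96 SE.
- Upper 95% limit = estimate + 1.96 SE, which lies between 0 and 3.92 SE.

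No SE is printed, so the limit cannot be located within that range.

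**5. Illustration only.** Assumptions: an unadjusted mean difference and the planned 26 per group (the analysed number is not printed).

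- SE = SD × √(2/26) = 0.277 SD, so the worst case is 3.92 × 0.277 = 1.09 SD of the marker change. It is 1.01 SD with 30 per group and 1.18 SD with 22.
- Power to detect a true shift of 0.2, 0.3 or 0.5 SD is about 11%, 19% or 44%. If the four markers were independent (a further assumption), all four would be non-significant with probability about 0.89⁴ = 0.63, 0.81⁴ = 0.43 or 0.56⁴ = 0.10.

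Under these assumptions, four non-significant results would be unsurprising even if every marker had worsened by 0.2 or 0.3 SD.

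**The case against.** The strongest reply is that the Results section is a short summary, the conclusion is hedged as a suggestion, and fuller marker results may be reported elsewhere. The last part stands, and the point is limited to this document for that reason. The hedge does not supply a missing bound, and the sentence on PWV and the markers is not hedged at all.

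Several stronger readings are tempting but not supported.

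- *That the conclusion ignores the PWV interval.* The estimate, interval and p-value stand in the same paragraph, so the reader has the bound. What is missing is a qualification in the conclusion.
- *That worsening of about 1.1 SD is likely for a marker.* That figure needs a p-value just above 0.05 in the harmful direction, and it uses a mean difference where the plan uses adjusted quantile regression. It shows what such a result can hide, not what these data show. Nothing here indicates harm.
- *That PWV safety is settled because the interval excludes 0.63 m/s.* That figure is an average benefit used for planning. The document does not justify it as a limit for harm, and the printed interval is for an adjusted median difference.
- *That the direction of the PWV difference is wholly open.* The fitness result points to exercise minus control; a label is needed to confirm it.

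Allocation by place of residence, adjustment for change in physical activity and the choice of analysis set are separate matters. This point does not depend on them.

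**Conclusion.** The marker part of the conclusion is unsupported as written. For hsCRP, TNF, IL-6 and MPO this document gives no estimate, interval or margin, so no limit on worsening can be stated for any of them. This follows from the text alone and needs none of the illustrative assumptions.

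The PWV part is a lesser fault of wording. The printed interval gives bounded support: the estimate is close to zero, and worsening beyond 0.36 m/s lies outside the 95% CI. Worsening up to 0.36 m/s is not excluded. This rests on the restored minus signs, which agree with the printed p-value, and on the difference being exercise minus control. Without a margin, the document gives no basis for calling 0.36 m/s acceptable or unacceptable.

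**What to change.** 1. Print the adjusted median difference and 95% CI for hsCRP, TNF, IL-6 and MPO from the quantile regressions that the Statistical Analysis section describes for the studied outcomes. Label the direction of every difference, including PWV.
2. Replace the opening statement of no differences with: *No between-group difference was detected.*
3. Remove the no-exacerbation clause. In its place write, for example: *No difference in PWV was detected (adjusted median difference -0.034 m/s, 95% CI -0.42 to 0.36, exercise minus control); worsening up to 0.36 m/s is not excluded. No difference was detected in hsCRP, TNF, IL-6 or MPO; estimates and 95% CIs are given above.* The authors should confirm the direction before using the 0.36 limit.
4. Make no claim of no worsening for any marker on p > 0.05 alone.

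No new data, model or margin is needed. The cost is a less favourable conclusion and a slightly longer results paragraph.
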